### 14.1 Sample size consideration

Inclusion of 20 men will allow for an 80% power to detect a response rate of greater than 15% in terms of sperm production and allow for a drop-out rate of 10% at an alpha of 0.05 (The primary outcome).

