	
including: Total cholesterol, HDL, LDL and fasting triglycerides at baseline, week 8, 16, 24 and 32 of treatment, and study exit. Additional measures will be conducted if any abnormal values are found until the end of study visit.
 
 
• Adverse event and concomitant medications throughout the study. Other safety parameters include vital signs; and changes in pre- and post-treatment physical examination results and score on the PHQ9 depression questionnaire.
 

Evaluations	
The following determinations will be made in all subjects:
 
 
• Semen analysis will be collected twice during screening and every four weeks during treatment and twice during recovery
 
• Serum samples will be collected for the measurement of: vitamin A, all-trans and 13-cis retinoic acid, testosterone, FSH and LH. Serum for these measures will be collected before the beginning of the treatment, and every two months during treatment and sy study exit.
 

Other Assessments	
Demographic characteristics, including age and race, will be collected.

Statistical Analysis	
The primary endpoint is the appearance of sperm in the ejaculate of treated men between baseline and 32 weeks. This analysis will be conducted using a Wilcoxon signed-rank test.

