## **9. Selection of Subjects**

### **9.1.1 Inclusion Criteria**

1. Subjects will be infertile men (no pregnancy with partner with normal cycles and normal hysterosalpingogram despite >1 year of unprotected intercourse).
2. Azoospermia (no sperm apparent in centrifuged semen) as assessed by semen analysis on two occasions separated by one week.
3. In the opinion of the investigator, is able to comply with the protocol, understand and sign an informed consent and HIPAA form.

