## 14. Statistical Considerations

**Data analysis and Interpretation of Results:** The primary endpoint is the presence of sperm in the ejaculate at week 32 of treatment compared with its absence at baseline. The presence of sperm after 32 weeks of treatment will be compared with baseline using a Wilcoxon sign-rank test. Linear regression will be performed to determine if significant relationships between baseline (or delta) serum concentrations of 13-cis retinoic acid and changes in sperm quality are present using STATA Version 10.0 (College Park, TX, USA). For all comparisons, an alpha of 0.05 will be considered significant.

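### The planned signed-rank test does not deliver the stated 80% power at a 15% response rate: power is at most 52% with 18 men and 60% with 20

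*Combined protocol and SAP*

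**What the plan says.** Section 14.1 gives the only justification for enrolling 20 men: "Inclusion of 20 men will allow for an 80% power to detect a response rate of greater than 15" percent. The sentence goes on to "allow for a drop-out rate of 10% at an alpha of 0.05 (The primary outcome").

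Section 14 defines a yes/no endpoint: "The primary endpoint is the presence of sperm in the ejaculate at week 32 of treatment compared with its absence at baseline". It then names the test: "The presence of sperm after 32 weeks of treatment will be compared with baseline using a Wilcoxon sign-rank test". The Synopsis agrees: "This analysis will be conducted using a Wilcoxon signed-rank test". On the significance level, Section 14 says "For all comparisons, an alpha of 0.05 will be considered significant".

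The entry criterion in Section 9.1.1 is "Azoospermia (no sperm apparent in centrifuged semen) as assessed by semen analysis on two occasions separated by one week". Section 13 rules out replacing men who have already taken study drug.

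The documents do not state whether the test is one- or two-sided, whether it is exact or large-sample, what null response rate is assumed, or which formula gave the 80%.

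**The concern.** The power statement and the primary test do not appear to belong together. Because every baseline is zero, each paired difference is zero (no sperm at week 32) or positive (sperm present). A signed-rank test on such data only counts responders, and it needs several of them before it can reach p < 0.05. With 18 men and a true rate of 15%, the expected number is 18 × 0.15 = 2.7, which is below every threshold the test could have.

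If so, a drug that truly works in 15% of these men would often give a non-significant result. Readers told that the trial had 80% power could then take that result as evidence of no effect.

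**Working it through.** **Inputs.** Enrolled: 20 (Sections 7 and 14.1). Drop-out: 10% (Section 14.1), without replacement of treated men (Section 13), so 20 × 0.9 = 18 evaluable. Alpha: 0.05 (Section 14). Response rate: 15%, the only rate stated (Section 14.1). Baseline: no sperm in any man (Section 9.1.1). Sidedness and test version are open, so all four combinations are shown.

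**Step 1: the test as a function of the number of responders, k.** There are k positive differences and none negative.

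- Exact: p = 0.5^k one-sided and 2 × 0.5^k two-sided.
- Large-sample with tie correction: the k differences all equal 1 and share rank (k+1)/2. The rank sum is k(k+1)/2, its null mean k(k+1)/4 and its null standard deviation (k+1)√k/4. Hence z = √k.

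**Step 2: smallest significant k.**

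- Exact two-sided: k = 5 gives 0.0625 and k = 6 gives 0.031, so 6 are needed.
- Exact one-sided: k = 4 gives 0.0625 and k = 5 gives 0.031, so 5 are needed.
- Large-sample two-sided: k = 3 gives 0.083 and k = 4 (z = 2.00) gives 0.0455, so 4 are needed.
- Large-sample one-sided: k = 2 gives 0.079 and k = 3 (z = 1.73) gives 0.042, so 3 are needed.

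Two responders are never enough.

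**Step 3: power at a true rate of 15%.** Power is P(X ≥ k) for X binomial(n, 0.15). For n = 18 the probabilities of 0, 1, 2, 3, 4 and 5 responders are 0.0536, 0.1705, 0.2556, 0.2405, 0.1592 and 0.0787. For example, P(X ≥ 3) = 1 − 0.0536 − 0.1705 − 0.2556 = 0.520.

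| Version of the test | k needed | Power, 18 men | Power, 20 men | True rate for 80% power, 18 / 20 men |
|---|---|---|---|---|
| Two-sided, exact | 6 | 4.2% | 6.7% | 40% / 37% |
| Two-sided, large-sample | 4 | 28.0% | 35.2% | 29% / 26% |
| One-sided, exact | 5 | 12.1% | 17.0% | 35% / 31% |
| One-sided, large-sample | 3 | 52.0% | 59.5% | 22% / 20% |

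**Step 4: other ways of running the signed-rank test.** Ranking sperm counts instead of presence leaves the exact thresholds unchanged. In the large-sample version with untied counts, keeping zeros in the ranking also leaves them unchanged (with 18 men, z = 1.995 at k = 4 and 1.730 at k = 3). Dropping zeros raises each threshold by one: k = 3 gives one-sided p = 0.054 and k = 4 gives two-sided p = 0.068. Power with 18 men is then 28.0% one-sided and 12.1% two-sided, so z = √k is the favourable case.

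**Step 5: can 80% be reached another way?** Only with a different test or added assumptions:

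- A rule of at least 2 responders: 77.6% with 18 men, 80.2% with 19, 82.4% with 20.
- A one-sample normal test against an assumed 2% null: 78.1% (two-sided) or 81.6% (one-sided) with 18 men.
- A one-sided arcsine formula for two independent groups of 20 without drop-out: 80.8%.

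None of these is the test in Section 14, and the documents do not say which calculation, if any of these, was used.

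**The case against.** Five points can be made for the plan.

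- **The rate is open-ended.** Section 14.1 speaks of a rate above 15%, and power rises with the rate. The Synopsis and Section 1 report that roughly half the men responded in the sponsor's earlier pilot. At a true 50%, 18 men give 95% power even if 6 responders are needed; at 30%, power runs from 47% to 94%. This is correct, and the trial is not underpowered for a large effect. But that pilot enrolled men with oligoasthenoteratozoospermia, Section 14.1 does not adopt its rate, and 15% is the only figure to which the 80% is attached.
- **15% could be the null rate.** Section 14 compares with absence at baseline, not with 15%. On this reading an exact one-sided test with 18 men needs 6 responders and a true rate of about 40% for 80% power. No such alternative is stated, so the 80% would still be unsupported.
- **The spread from 4% to 52% comes from choices the plan leaves open.** That is fair. The conclusion that does not depend on them is that the best case is 52% with 18 men or 60% with 20.
- **It is an open-label, single-arm pilot with no go/no-go rule.** A pilot need not claim power. This one states a power, an alpha and a significance test, so they should agree.
- **The signed-rank test suits this endpoint poorly**, since no difference can be negative, and a response proportion with an exact confidence interval would be simpler. This stands as a comment on the choice of analysis. It does not repair the power sentence.

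**Conclusion.** The concern holds. Under no version of the planned test does power at a 15% response rate reach 80%, with 18 or 20 men. The most favourable combination (one-sided, large-sample, tie-corrected, no drop-out) is 80 − 59.5 = 20.5 points short. With the planned drop-out, three of the four versions would give p > 0.05 more often than not, and the fourth succeeds 52% of the time.

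For scale, 80% power at 15% would take 28 to 52 evaluable men, depending on the version.

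The result assumes that 15% is the rate to be detected, that drop-out leaves 18 evaluable men, and that the test compares week 32 with an all-zero baseline. Sidedness and test version change the size of the shortfall but not its existence. Because this sentence is the sole basis for the sample size and concerns the primary outcome, it must be corrected.

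**What to change.** Keep enrolment at 20. In Section 14, state the sidedness and the version of the primary test, and restate Section 14.1 to match. Possible wording:

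- *If two-sided:* With 18 evaluable men and two-sided alpha 0.05, the signed-rank test has 80% power only for a true response rate of about 40% (exact) or 29% (large-sample); power at 15% is 4% or 28%.
- *If one-sided:* The corresponding rates are about 35% (exact) or 22% (large-sample); power at 15% is 12% or 52%.

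Only the clause for the chosen version should remain.

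If the sponsor prefers power near 80% at 15%, an exact binomial test with success at 2 or more responders gives 78% with 18 men and 82% with 20. It must then replace the signed-rank test in Section 14 and the Synopsis. The background (spontaneous) rate must be written down as an assumption, because the documents give none. Type I error of that rule with 18 / 20 men is:

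- 1.4% / 1.7% at an assumed background of 1%
- 5.0% / 6.0% at 2%
- 10.0% / 12.0% at 3%

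It keeps one-sided 0.05 only up to a background rate of about 2.0% (18 men) or 1.8% (20 men).

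The cost is one reworded paragraph and one added clause, with a less favourable stated power. The binomial route keeps the power but makes the result depend on the assumed background rate. Neither needs more patients or any change to clinical procedures.

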### 14.2 Efficacy

The primary efficacy outcome is the presence of sperm in the ejaculate of formerly azoospermic men.

### 14.3 Safety

Laboratory data, physical examination results, vital signs and chemistry levels will be assessed and compared for each subject from screening to end of study. All adverse events will be recorded and coded using the body system coding of MedDRA.

The incidence of adverse events will be examined by using descriptive statistics. Clinical chemistries and allied data will be examined for change over time.

### 15. Adverse Events

Adverse Events (AE) will be carefully monitored and an AE form is included in the CRF. Serious adverse events (SAE) as defined below will be reported on the SAE form included as appendix #3.

All adverse experiences must be recorded in the study event record of the subject's CRF, and will include the following information (when applicable):

- Specific condition or event
- Indication of whether the condition was pre-existing or not and if yes, whether it has worsened in severity (including an increase in frequency)
- Date of occurrence
- Date of resolution
- Relationship to study drug as evaluated by the investigator (causality assessment). The investigator must enter their opinion of causality on the AE forms.
- Action taken (study drug continued or not) and outcome
- Seriousness according to the approved regulatory classification {i.e. any event that is fatal, life-threatening, disabling, incapacitating, results in or prolongs hospitalization, or is a medically significant event, e.g. an intervention to prevent one of the above outcomes, or any other serious criteria (cancer, congenital anomaly, overdose, other significant) is considered serious}.

**When any serious adverse drug experience, regardless of causality, is encountered during this clinical trial at an investigator's site, the investigator must notify the Study Monitor by facsimile using the form provided as an appendix. This report must be submitted within 2 calendar days from the time the investigator's staff is notified of the event.**

All serious adverse events that are unexpected will be reported to the FDA by the principal investigator or his designated surrogate. All serious adverse events will be followed until fully characterized. The investigator will collect and forward to the FDA via fax, all available supporting documentation (with subject name redacted) for serious events, including at a minimum hospital discharge summaries and death certificates (where applicable). Additional supporting documentation that should be collected whenever possible, to verify the medical diagnosis, includes autopsy reports (where applicable), surgical procedure summaries, histology reports, and imaging reports.

## **16. Ethical Considerations**

### **16.1 Informed Consent**

Principal investigators will provide the NICHD with a copy of the Informed Consent approved by their local Institutional Review Board (IRB). The Informed Consent will be translated and certified into the language of the respondent as needed.

Under this consent, the subject shall understand that he is authorizing access to medical records as required for monitors, auditors, IRBs and regulatory authorities.

### **16.2 Conflicts of Interest**

The investigators will not profit from results, either positive or negative, with regard to the product being evaluated.

### **16.3 Subject Recruitment**

The subjects will be recruited from UW and Community Infertility and Urology clinics who see >200 such men annually. The study coordinator will screen potential subjects over the phone by inquiring about their age and medical history. Potential subjects who qualify by phone screen will be scheduled for an appointment to consult with the investigator about further eligibility requirements for the study.

## **17. Confidentiality**

The information on individual subjects arising from this study is to be considered confidential and transmitted to the sponsor only in a form that will not permit identification of the individual. Regulatory and sponsoring agencies may request access to the study records and related medical records of each participating subject, and if requested, the subject's identity will remain confidential to the extent permitted by the applicable laws and regulations. All records will be kept in a secure storage area with limited access.

## **18. Investigative Record Management**

All investigative site records will be kept in a secure storage area with limited access. NICHD should be notified before destruction of any site records.

## **19. Data Transmission**

Not applicable

## **20. Publication Policy**

Data on the use of the study drug and results of all clinical and laboratory studies are considered private and confidential. NICHD will encourage publication of the results of the study.

## **21. Investigator Documentation**

Prior to beginning the study, the investigator will be asked to demonstrate compliance with ICH E6, 8.2 and 21 CFR 312 by providing the following essential documents, including but not limited to:

1. An Institutional Review Board (IRB) -approved Informed Consent (as described in section 18.1) in the local language.
2. Local IRB approval.
3. Form FDA 1572, fully executed, and all updates on a new fully executed Form FDA 1572.
4. Current curriculum vitae (CV) for each principal investigator and each sub investigator listed on Form FDA 1572.

### Appendix 1: Schedule of Events

	Visit #	Screening		Treatment		Follow-up	
		S1	S2	T1	T2-T9	F1	F2/exit
		Study Day	-60 to -1	-53 to 1	1	Wks: 4, 8,12,16, 20, 24, 28, 32	Wk 44
Administrative	Informed consent/HIPAA	X					
	Vital Signs	X	X	X	X	X	X
Medical	Medical History	X					
	Physical Exam	X		X	X	X	X
	AE & Con Med	X	X	X	X	X	X
	Semen Analysis	X	X	X	X	X	X
	PHQ9 Questionnaire	X		X	X	X	X
Blood Sampling	CBC,Chemistry/Lipids, CK	X		X	X**	X	X
	FSH, LH, T & Retinoids	X		X	X**	X	X
Drug Administration	Dispense Study Meds			X	X*		
	Dispense study med log			X	X		
	Collect and review med log				X		
	Collect unused study meds				X		
Reimbursement (\$)		30	20	40	40	30	30

- Visit T9, week 32: No drug dispense \*\*Blood draws only week 8, 16, 24 and 32

- **Abbreviations:**
- HIPAA: Health insurance portability and accountability act
- PHQ9: Patient health questionnaire, #9
- FSH: follicle-stimulating hormone
- LH: luteinizing hormone
- T: testosterone
- AE: adverse event
- Con Med: concomitant medications
- S1/S2: screening visit 1/2
- T1-T7: treatment visits 1-7
- F1/F2: follow-up visit 1/2
- Wk: week

Appendix 2: PHQ9 Questionnaire

**PATIENT HEALTH QUESTIONNAIRE (PHQ-9)**

NAME: \_\_\_\_\_ DATE: \_\_\_\_\_

Over the last 2 weeks, how often have you been bothered by any of the following problems?  
(use "✓" to indicate your answer)

	Not at all	Several days	More than half the days	Nearly every day
1. Little interest or pleasure in doing things	0	1	2	3
2. Feeling down, depressed, or hopeless	0	1	2	3
3. Trouble falling or staying asleep, or sleeping too much	0	1	2	3
4. Feeling tired or having little energy	0	1	2	3
5. Poor appetite or overeating	0	1	2	3
6. Feeling bad about yourself—or that you are a failure or have let yourself or your family down	0	1	2	3
7. Trouble concentrating on things, such as reading the newspaper or watching television	0	1	2	3
8. Moving or speaking so slowly that other people could have noticed. Or the opposite—being so fidgety or restless that you have been moving around a lot more than usual	0	1	2	3
9. Thoughts that you would be better off dead, or of hurting yourself	0	1	2	3

add columns  +  +

(Healthcare professional: For interpretation of TOTAL, TOTAL:   
please refer to accompanying scoring card).

10. If you checked off any problems , how difficult have these problems made it for you to do your work, take care of things at home, or get along with other people?	Not difficult at all	_____
	Somewhat difficult	_____
	Very difficult	_____
	Extremely difficult	_____

Copyright © 1999 Pfizer Inc. All rights reserved. Reproduced with permission. PRIME-MD® is a trademark of Pfizer Inc. A2663B 10-04-2005

**Appendix 3: Serious Adverse Event Report Form**

SERIOUS ADVERSE EVENT REPORT				CBR SERIAL NO:		
I. EVENT INFORMATION						
1. PATIENT INITIALS	1.a COUNTR Y	2. DATE OF BIRTH Day      Month Year	2.a. AG E  year s	3. SE X	3.a. HEIGHT  cm	3.b. WEIG HT  kg
7.- 13. DESCRIBE EVENT. _____EXPECTED UNEXPECTED					4.-6. EVENT ONSET Day Month Year	
DIAGNOSIS: ..... Description:					_____ 8.-12. SERIOUSNESS CRITERIA CHECK ALL APPROPRIATE TO EVENT _____DEATH (DATE) Day      Month Year _____HOSPITALIZATION _____DISABILITY OR INCAPACITY _____LIFE-THREATENING _____OTHER SERIOUS CRITERIA (Cancer, congenital anomaly, overdose, significant) _____NOT APPLICABLE	
II. SUSPECT DRUG INFORMATION						
14. SUSPECTED DRUG(S) (include generic name(s))				20. DID EVENT ABATE AFTER STOPPING DRUG? ____YES ____NO ____NOT APPLICABLE		
15. DAILY DOSE (include schedule)		16. ROUTE OF ADMINISTRATION				

17. INDICATION(S) FOR USE		21. DID EVENT RE-APPEAR AFTER REINTRODUCTION?	
18. THERAPY DATES (from/to) Day Month Year Day Month Year		19. THERAPY DURATION UNTIL REACTION ONSET	
		 YES  NO  NOT APPLICABLE	
III. CONCOMITANT DRUGS AND HISTORY			
22. CONCOMITANT DRUGS AND DATES OF ADMINISTRATION (exclude those used to treat reaction)			
23. OTHER RELEVANT HISTORY (e.g. diseases, allergies, pregnancy etc.)			
IV. IND HOLDER INFORMATION		V. INVESTIGATOR'S ASSESSMENT	
24.a. NAME AND ADDRESS OF IND HOLDER Population Council Center for Biomedical Research [name] USA [contact]		23.d. OUTCOME  Recovered  Recovering  Not Recovered  Sequelae  Fatal  Unknown	
24.b. PATIENT IDENTIFIER NO		23.e. CAUSALITY  Not Related  Unlikely  Possible  Probable  Highly Probable  Insufficient Data	
24.c. DATE RECEIVED Day Month Year		24.d. TRIAL NUMBER	
24.e. DATE OF THIS REPORT Day Month Year		25.a. REPORT TYPE  INITIAL  FOLLOW-UP	
26. NAME AND ADDRESS OF REPORTING PHYSICIAN			

Add another page if not sufficient space. If this case is from literature, please attach an original article
